- External monitoring is performed by an independent Clinical Research Associate (CRA), which provides regular site monitoring and data validation to ensure data quality and patient safety.
- The Data Safety Monitoring Board (DSMB) periodically reviews accumulated safety data, including adverse event frequencies and severity, to address any unexpected risks promptly.

Substudies

The following substudies are planned:

- Echocardiographic substudy,
- Magnetic Resonance Imaging substudy.

Subgroup analysis

The analysis of the following subgroups is planned in the study:

- Women versus men,
- Patients with prehospital time delay duration 3 hours and longer versus less than 3 hours,
- Patients with and without out-of-hospital cardiac arrest,
- Patients with and without mechanical ventilation,
- Patients with and without mechanical circulatory support (e.g., IMPELLA, ECMO)*
- Patients with and without persistent coma (Glasgow Coma Scale < 8) at admission,
- Patients with and without diabetes,
- Patients with and without obesity,
- Patients who are cigarette smokers versus non-smokers,
- Patients with and without multivessel disease,
- Patients with and without a history of heart failure.

**A time-dependent covariate analysis will be performed instead of standard subgroup analysis to prevent bias due to treatment-dependent selection effects for mechanical circulatory support (MCS), which may occur post-randomization.*

Handling of Post-Randomization Events (MCS)

MCS use will be modeled as time-dependent covariates in survival analyses to avoid bias introduced by post-randomization treatment effects. These covariates will be introduced into the primary and secondary outcome models as follows:

Time-Dependent Covariate Analysis

To accurately account for the influence of MCS on study outcomes, these variables will be modeled as time-dependent covariates within the Cox proportional hazards model:

Primary Model:

- $HR = \beta_1(\text{Treatment}) + \beta_2(\text{Mechanical Ventilation (time-dependent)}) + \beta_3(\text{ECMO (time-dependent)}) + \epsilon$
- This ensures that the estimation of treatment effects is not confounded by patients who deteriorate and need additional support after randomization.

Competing Risks Model (Fine & Gray) for Non-MACE Outcomes:

- If MCS is strongly associated with mortality before the primary endpoint, a competing risks approach will be applied using the Fine & Gray subdistribution hazard model.

Sensitivity Analysis

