Standard descriptive statistics will be employed in the analysis to summarize both categorical and continuous variables. For categorical variables, data will be presented as absolute frequencies (i.e., counts) and relative frequencies (i.e., percentages), clearly representing each category's distribution across the study groups. For continuous variables (including pharma-economic data), the data will be reported either as the median supplemented with the interquartile range (IQR) or the 5th to 95th percentiles range, which captures the central tendency and spread in a non-parametric manner or as the mean supplemented with the standard deviation, which provides a measure of central tendency and variability under the assumption of normal distribution. The choice between median and mean reporting will depend on the distributional properties of the continuous variables. Data visualization will use standard box and whisker plots for continuous variables and bar plots for categorical variables. Relative risks and 95% confidence intervals will be used to describe and visualize the results of endpoint analysis.

The chi-square test will be employed for categorical variables, including the primary and secondary study endpoints and all other relevant categorical data, to assess the statistical significance of observed differences between groups. This test will evaluate whether the observed frequencies in different categories deviate from what would be expected under the null hypothesis. The Mann-Whitney U test will be applied for continuous variables, as it is a robust non-parametric alternative to the t-test, particularly useful when the assumption of normality is not met. This test will determine whether there are statistically significant differences in the distribution of continuous variables between the study arms. The non-inferiority scenario will be assessed using a one-sided Z-test with a non-inferiority margin of 1%.

To ensure comparability among centers, the data for analyzing maximum values of high-sensitivity cardiac troponin will be presented as the ratio of the maximum value within seven days to the reference value for myocardial infarction at a specific center.

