A p-value of 0.05 will be adopted as the threshold for determining statistical significance across all analyses. All statistical analyses will be conducted in strict accordance with the regulatory guidelines outlined in the E9 Statistical Principles for Clinical Trials document published by the U.S. Food and Drug Administration (FDA) under the reference FDA-1997-D-0508. These guidelines ensure that the statistical methods employed adhere to established clinical trial data analysis standards, ensuring rigor, reproducibility, and validity of findings.

Variables and tables will be presented in the order in which the sections are shown in the eCRF. Parameters recorded in more than one SI unit (e.g., lab units) will be converted into a single SI unit as appropriate.

Description of patients' characteristics

Prior to the analysis of the primary and secondary endpoints, the treatment groups (or any groups in subgroup analyses) will be compared about the following patients' characteristics:

- Demographics: age, sex, body weight, body mass index (BMI), obesity, and cigarette smoking.
- Characteristics of AMI at admission: type of acute myocardial infarction (STE- or NSTEMI), mechanical ventilation upon admission.
- Time delay: from symptoms to hospital, from symptoms to reperfusion.
- Out-of-hospital cardiac arrest: cardiopulmonary resuscitation before admission, first documented rhythm, time to return of spontaneous circulation (ROSC) (min), external cardiac massage - before admission, on admission, overall duration, mechanical ventilation, regulation of body temperature, target value.
- Patient's status at the time of admission: blood pressure - left arm systolic/diastolic (mmHg), blood pressure - right arm systolic/diastolic (mmHg), pulse rate (BPM), cyanosis, mydriasis, transient mydriasis, deep unconsciousness without prior treatment with hypnotics.
- Treatment with vasopressors and/or inotropic agents, noradrenaline, adrenaline, dopamine, dobutamine, another vasopressor agent, another inotropic agent.
- Analgosedation: analgosedation, opioid (morphine, fentanyl, sufentanil), benzodiazepine (midazolam, diazepam, other), propofol, another analgosedation method.

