- Medical history: hyperlipidemia, hypertension, diabetes mellitus, previous myocardial infarction, previous PCI, previous CABG surgery, previous implantation of a pacemaker, ICD, CRT, chronic heart failure, chronic kidney failure, chronic liver failure, Child-Pugh score, peripheral vascular disease, peripheral artery bypass, history of bleeding, chronic obstructive pulmonary disease.
- Chronic medication: aspirin, clopidogrel, prasugrel, ticagrelor, beta-blocker, ACE inhibitor, ARB, ARNI, statin or another lipid-lowering agent, furosemide, hydrochlorothiazide (indicated as a diuretic agent), spironolactone, digoxin, ivabradine, proton-pump inhibitors.
- Echocardiography during the admission or first day of hospitalization: LVEF (%), complications of MI: ventricular septal defect, ruptured mitral chordae tendineae, and severe mitral regurgitation; hemodynamically significant pericardial effusion, other.
- Coronary angiography: approach, number of affected vessels, left main coronary artery disease (LMCAD), indication after coronary angiography.

- Percutaneous coronary intervention: artery treated during the PCI: left main coronary artery, left anterior descending artery (ramus diagonalis), circumflex artery (ramus marginalis sinister), right coronary artery; PTCA only; stent implantation: number, total length of stented segments (estimate) in mm, BMS, DES, BVS, another stent; TIMI flow grade through the infarct-related artery before PCI, TIMI flow grade through the infarct-related artery after PCI; complications of PCI; evaluation of the procedural result (optimal, suboptimal, failed PCI); Comment on the procedure.
- Laboratory tests during the visit examination: hemoglobin (Hb) (g/L), hematocrit (HCT) (%), erythrocyte count (RBC) ($\times 10^{12}/L$), leukocyte count (WBC) ($\times 10^9/L$), platelet count (PLT) ($\times 10^9/L$), urea (mmol/L), creatinine (mmol/L), glycemia (mmol/L), AST (ukat/L), ALT (ukat/L), lactate (mmol/L), CRP (mg/L), ratio of value of high-sensitive cardiac troponin and reference value for MI, total bilirubin ($\mu\text{mol}/L$), Na (mmol/L), K (mmol/L), arterial blood gas (ABG) pH, pO_2 (kPa), pCO_2 (kPa), base excess (BE) (mmol/L).

Additional analyses

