The analysis of the primary and secondary endpoints in the complete study population assumes a balanced distribution of potentially confounding factors between the study arms, which is expected to be achieved through randomization. Considering this assumption, no prior planned multivariate adjustment for the confounding variables will be conducted in the initial analysis of the primary endpoints. However, despite this, further exploratory analyses will incorporate both univariate and multivariate models, such as logistic regression and Cox proportional hazards models, to evaluate the potential influence of specific patient characteristics on the occurrence of the endpoints. This approach will provide a more detailed understanding of how individual baseline factors may affect study outcomes. Additionally, time-to-event data will be visualized using the Kaplan-Meier methodology, allowing for an informative representation of the temporal aspects of endpoint occurrences. Time to the event will be computed from the date of randomization and the date of the analyzed event or the date of last contact in the case of censored patients.

For subgroup analyses, where confounding factors may exhibit an unbalanced distribution across the study arms, they will be incorporated into the multivariate logistic regression models. This will allow for appropriate adjustment for these confounders, providing a more accurate estimation of the association between treatment effects and study endpoints in the presence of imbalances. By accounting for such factors, the analysis will enhance the robustness and validity of the conclusions drawn regarding the study outcomes within the specified subgroups.

Safety analysis

This phase IV clinical trial focuses on observing and comparing the use of approved medicinal products as part of standard clinical practice. Information regarding side effects will neither be actively collected nor evaluated.

Hospitalizations and life-threatening conditions, which are prerequisites for study enrollment, are not categorized as serious adverse events (SAEs). The investigator will perform causality assessments, and immediate reporting of adverse events unrelated to the study will not be required.

In routine clinical practice, cardiogenic shock has a mortality rate of over 50%. Deaths unrelated to the study will be summarized and included in annual study reports.

References

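### Subgroup analyses have no treatment-by-subgroup test, adjust for covariates by observed imbalance with no fixed list, and leave the forest-plot measure unnamed

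*SAP*

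**What the plan says.** The list under Subgroup analysis opens with "The analysis of the following subgroups is planned in the study" and names 11 factors. One of them, mechanical circulatory support (MCS), is taken out of the standard subgroup approach and given a time-dependent Cox analysis, which leaves 10.

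The method for the others is in Additional analyses: "where confounding factors may exhibit an unbalanced distribution across the study arms, they will be incorporated into the multivariate logistic regression models". The same paragraph says that this adjustment is meant to strengthen conclusions within the subgroups. No covariates are named and no degree of imbalance is defined.

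Imbalance would be seen in the comparison set out under Description of patients' characteristics, where "the treatment groups (or any groups in subgroup analyses) will be compared about the following patients' characteristics". That list is long and includes "TIMI flow grade through the infarct-related artery after PCI; complications of PCI; evaluation of the procedural result".

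The overall analysis is of another kind. Under Statistical analysis, "The chi-square test will be employed for categorical variables, including the primary and secondary study endpoints", and "Relative risks and 95% confidence intervals will be used to describe and visualize the results of endpoint analysis". Additional analyses adds that "no prior planned multivariate adjustment for the confounding variables will be conducted in the initial analysis of the primary endpoints".

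The significance rule is general: "A p-value of 0.05 will be adopted as the threshold for determining statistical significance across all analyses". Reporting & Interpretation limits forest plots to pre-randomisation subgroups but does not say what measure they show. No treatment-by-subgroup interaction test appears anywhere in the SAP.

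**The concern.** A subgroup analysis asks whether the treatment effect differs between, say, patients with and without out-of-hospital cardiac arrest. The plan does not test that. It models the effect within subgroups, applies 0.05 to the result, and leaves the reader to compare two verdicts. Significant in one half and not in the other is not evidence of a difference.

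Three features make the comparison less secure:

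- The covariates are settled only after the arms have been compared, which leaves the analyst a choice.
- Some candidates, such as flow after PCI and procedural result, can be affected by the study drug. Adjusting for them can remove part of the treatment effect or bias it. The SAP recognises this problem for MCS but leaves it open here.
- Logistic models give odds ratios, while the overall result is a relative risk. If the forest plots carry the adjusted odds ratios, the subgroup effects will look stronger than the overall one.

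At stake is a claim in the trial report that cangrelor works in some patients with cardiogenic shock and not in others.

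**Working it through.** **Inputs.** From Power analysis for the superiority scenario: control 50%, cangrelor 38%, power 0.8, significance level 0.05 (taken as two-sided), total 536. From Randomization: 1:1 allocation. Subgroup splits of 50/50 and 25/75 are assumptions, because the SAP gives no prevalences.

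**1. The plan's own figure.** With mean rate 0.44:

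n per arm = [1.960·√(2·0.44·0.56) + 0.8416·√(0.50·0.50 + 0.38·0.62)]² / 0.12² = (1.3759 + 0.5865)² / 0.0144 = 267.4, rounded up to 268. The total is 536, as stated.

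**2. Scale.** RR = 0.38/0.50 = 0.76. OR = (0.38/0.62)/(0.50/0.50) = 0.61. If the RR were 0.76 in every subgroup, the OR would still vary with control risk (risks assumed):
- at 30%: (0.228/0.772)/(0.30/0.70) = 0.69
- at 70%: (0.532/0.468)/(0.70/0.30) = 0.49

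**3. Covariate choice.** Hold the unadjusted OR at 0.613 and add a perfectly balanced binary covariate with 50% prevalence. The adjusted OR becomes 0.604, 0.577, 0.533 or 0.473 when the covariate's own OR is 2, 4, 8 or 16 (assumed). The shift is small unless the covariate is very strongly prognostic.

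**4. Same true effect in both halves.** Power with n per arm = Φ{[0.12·√n − 1.3759]/0.6969}.
- 50/50 split, n = 134: Φ(0.019) = 0.508 in each half. One half significant and the other not: 2·0.508·0.492 = 0.50.
- 25/75 split, n = 67 and 201: Φ(−0.565) = 0.286 and Φ(0.467) = 0.680. Discordant: 0.286·0.320 + 0.680·0.714 = 0.58.

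An interaction test at 0.05 would signal a difference in about 5% of such trials.

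**5. Power of the interaction test.** The variance of the log OR in one half of a 50/50 split is 1/(134·0.25) + 1/(134·0.2356) = 0.0615. The SE of the difference is √(2·0.0615) = 0.351. For an interaction as large as the planned log OR, |ln 0.613| = 0.490, power = Φ(0.490/0.351 − 1.96) = Φ(−0.56) = 0.29. For one twice as large, power is about 0.80. In a 25/75 split the corresponding figures are about 0.23 and 0.68.

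**6. Multiplicity.** In 4,000 simulated trials with no treatment effect (N = 536, 45% event rate, 10 independent binary factors with assumed prevalences of 15% to 60%), at least one within-subgroup test fell below 0.05 in about 43%. At least one interaction test did so in about 41%.

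**The case against.** The covariate sentence can be read more mildly: subgroups in general may be unbalanced, so confounders will be adjusted for. On that reading nothing is selected on observed imbalance and the list is merely missing. The phrasing about adjustment in the presence of imbalances, together with the planned comparison of groups within subgroup analyses, favours the stricter reading. Under either, the covariates are not fixed in advance.

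A reader might infer that the two halves of a subgroup pair will be adjusted for different covariates. The SAP does not say so, and one model per factor is equally compatible with its wording.

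A reader might also infer that the forest plots will show odds ratios. The relative-risk sentence is general and does not exclude subgroups, so forest plots of relative risks would fit the plan. What stands is that the measure is not named.

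Harm from the imbalance rule itself may be modest. In a simulated subgroup of 268 patients with 10 binary covariates, four of them prognostic (OR 2 or 4) and entered when imbalance had p < 0.10 (all assumed), null rejection stayed at 4% to 5%. The mean absolute shift in the treatment log OR was 0.035 to 0.057, against a sampling SD of about 0.25. This answers a claim of large covariate-driven distortion. It does not cover deliberate choice, very strong predictors or post-treatment covariates.

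Finally, interaction tests hardly change the chance of some false positive (41% against 43%). That is correct: the case for them is that they answer the right question.

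**Conclusion.** The concern stands as a weakness of the subgroup plan. It specifies no test of whether the effect differs between subgroups, no fixed covariates, no bar on post-treatment covariates and no named measure for the forest plots, while the 0.05 threshold applies throughout.

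The main consequence is the discordance figure. With an identical true effect at the planned rates, one half of a 50/50 subgroup is significant and the other is not in about 50% of trials (58% for a 25/75 split). This rests on the SAP's rates and N, on the assumed splits, and on the same event rates in both halves. The possible gap between an odds ratio of 0.61 and a relative risk of 0.76 arises only if the two measures are shown side by side, which the SAP neither plans nor rules out.

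The count of 10 factors takes mechanical ventilation as status at admission; the SAP also enters it as time-dependent in its Cox model.

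A reader might infer that the main result is in doubt. It is not: the primary test and sample size do not depend on the subgroup models.

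**What to change.** Replace the subgroup paragraph in Additional analyses with the following:

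- For each pre-randomisation factor, fit one model with treatment, subgroup and treatment-by-subgroup interaction. MCS stays with its separate time-dependent analysis.
- Report each subgroup's relative risk with 95% CI, on the same scale as the overall result, with the interaction estimate, its CI and p-value. Name the relative risk as the forest-plot measure.
- Use no covariates, or one fixed set of pre-randomisation covariates named in the SAP and used for every factor. Delete the imbalance rule.
- State that within-subgroup p-values support no claim and that the subgroup results are descriptive.

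The cost is SAP wording; no new data are needed. Subgroup statements become more cautious, because the interaction test has only about 29% power for an interaction as large as the planned log odds ratio in a 50/50 split. Nor does it control multiplicity: about a 41% chance of at least one false positive across 10 factors remains.

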The dual approach of automated electronic validation through TrialDB and manual verification by a monitor and investigating team aims to uphold the highest data quality standards, ensuring that the data submitted for analysis are accurate and reliable, thereby enhancing the overall integrity of the study findings. The final validation of endpoints is provided by the endpoint adjudication committee and approved by its chairperson. Each endpoint is evaluated by two independent experts, with a third expert resolving any disagreements, ensuring robust and unbiased endpoint classification.

Statistical analysis

Statistical software and responsibilities

The data will be reviewed and statistically processed in the statistical analysis center: Institute of Biostatistics and Analyses, Faculty of Medicine, Masaryk University, Brno, [name], MS.c. Ph.D. The analysis will be computed using SPSS 27.0.1 (IBM Corporation, 2021).

Handling of missing values and outliers

Missing values are subject to validation procedures and will be communicated with study sites using lists of detected problems. If correction of missing values is not possible, no imputation of missing values will be performed. The presence of outliers will be evaluated using visual inspection of the continuous variable distribution; detected outliers will be removed from the statistical computations.

Interim analysis

No interim analysis is planned for this study; the decision can be justified as follows:

Reduction of Type I Error: Conducting interim analyses introduces the risk of inflating the Type I error rate. By avoiding interim analyses, the SAP maintains the integrity of the statistical significance threshold (e.g., a p-value of 0.05).

Pragmatic Feasibility: Given the acute nature of myocardial infarction with cardiogenic shock, the timeline for endpoint occurrences (30 days for primary endpoints) is relatively short, reducing the value of interim results for decision-making purposes.

Cost and Logistical Considerations: Implementing interim analyses would require additional resources, such as re-randomization schemes, database locks, and independent review committees, which are unjustified given the study's endpoints and anticipated outcomes timeline.

To mitigate risks associated with the absence of interim analysis:

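### The no-imputation rule makes no exception for baseline covariates, so the subgroup-adjusted and exploratory models lose randomized patients whose arm and outcome are known

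*SAP*

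**What the plan says.** SAP, Handling of missing values and outliers, sets one rule for all variables: "If correction of missing values is not possible, no imputation of missing values will be performed". The same section says of continuous variables that "detected outliers will be removed from the statistical computations". Neither rule separates outcomes from covariates.

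SAP, Additional analyses, leaves the initial analysis of the primary endpoints unadjusted. It then states that "further exploratory analyses will incorporate both univariate and multivariate models, such as logistic regression and Cox proportional hazards models". For subgroup analyses, confounders that are unbalanced between the arms are handled as follows: "they will be incorporated into the multivariate logistic regression models". The covariates are not named.

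SAP, Description of patients' characteristics, lists the items on which groups, including subgroups, are compared before the endpoint analysis. They include laboratory values, blood gases, medical history and an echocardiogram taken up to the first day in hospital. Some can exist only for some patients: time to return of circulation after an arrest and, presumably, the second item in "chronic liver failure, Child-Pugh score".

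SAP, Statistical software and responsibilities, names the package ("The analysis will be computed using SPSS 27.0.1"). No section gives another way to keep a patient whose covariate is blank, such as a missing category or indicator.

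**The concern.** A logistic or Cox model cannot use a patient with a blank covariate unless something is put in its place. If nothing may be put there, the patient leaves the model although the arm and the outcome are known. The SAP does not use the term complete-case analysis, but that is what the rule produces in a standard fit.

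Two things are at stake. Subgroup estimates, already based on few patients, become less precise, although Additional analyses presents the adjustment as a way to make them more accurate and robust. And because each model has its own covariates, each has its own sample, so adjusted and unadjusted results, or two adjusted models, no longer describe the same patients. The outlier rule can add to the loss, since a removed continuous value is one more blank.

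The point concerns blank covariates in patients whose outcome is known. Missing outcomes are a separate matter.

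**Working it through.** **Inputs from the SAP.** Event rates of 50% and 38%, significance level 0.05, power 0.80, 536 patients, 550 after drop-out (Sample size calculation); 1:1 allocation (Randomization). The SAP gives no covariate count and no missingness rate; those below are assumptions.

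**The plan's own figure.** With pooled variance, two-sided 0.05 and no continuity correction:

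n per arm = [1.960 x sqrt(2 x 0.44 x 0.56) + 0.8416 x sqrt(0.50 x 0.50 + 0.38 x 0.62)]^2 / 0.12^2 = 268, total 536, as stated. Then 536/0.97 = 553 against the stated 550, a difference that does not matter here. I use 550 as the base. This sample size belongs to the unadjusted test and is not affected by the point.

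**Precision.** If k covariates are each blank with probability m, independently, the share kept is f = (1 - m)^k. Relative to a model that keeps everyone, the standard error grows by about 1/sqrt(f).

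| k | m | f | kept of 550 | SE factor |
|---|---|---|---|---|
| 5 | 2% | 0.904 | 497 | 1.05 |
| 5 | 5% | 0.774 | 426 | 1.14 |
| 10 | 2% | 0.817 | 449 | 1.11 |
| 10 | 5% | 0.599 | 329 | 1.29 |

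In an assumed subgroup of one quarter of 536, that is 134 patients, the last row leaves 134 x 0.599 = 80.

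**Clustering.** Independence is the unfavourable end. If all blanks fell in the same patients, f = 1 - m whatever k is. At m = 5%, f = 0.95, about 523 of 550 remain and the factor is 1/sqrt(0.95) = 1.03. With 10 covariates at 5%, the range is therefore 1.03 to 1.29, depending on how far blanks cluster.

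**Does selective loss of events bias the treatment effect?** Assume some covariate is blank in 30% of patients with an event and 5% of those without, equally in both arms.

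- Control: 0.50 x 0.70 = 0.350 and 0.50 x 0.95 = 0.475; observed risk 0.350/0.825 = 42.4%.
- Cangrelor: 0.38 x 0.70 = 0.266 and 0.62 x 0.95 = 0.589; observed risk 0.266/0.855 = 31.1%.
- Patients kept: 275 x 0.825 + 275 x 0.855 = 462. Events kept: 275 x (0.350 + 0.266) = 169, of 275 x 0.88 = 242.
- Odds ratio before: (0.38/0.62)/(0.50/0.50) = 0.613. After: (0.266/0.589)/(0.350/0.475) = 0.613.
- Risk ratio: 0.76 before, 0.311/0.424 = 0.73 after.
- Standard error of the log odds ratio: x1.12.

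The retention factors 0.70 and 0.95 cancel from the odds ratio. Absolute risks, the risk ratio and precision change. The cancellation is shown for the odds ratio only; it does not by itself cover hazard ratios from the exploratory Cox models.

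The odds ratio moves only if blanks also depend on arm. With 30% blank among control events, 20% among cangrelor events and 5% among patients without an event, it becomes (0.38 x 0.80/0.589)/(0.350/0.475) = 0.70.

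**The case against.** A reader might infer that the rule removes early deaths selectively and so biases the treatment effect. Patients who die within hours may well lack an echocardiogram or laboratory values, but the SAP does not show it. Even if it happens, equal dependence on outcome in both arms leaves the odds ratio unchanged, and the subgroup models are logistic. The shift to 0.70 needs dependence on arm, for which the SAP gives no basis.

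A reader might also infer that everyone without an arrest or without liver disease drops out. Nothing says those items will enter a whole-population model. That covariates come from the list of patient characteristics is a reasonable inference, not a statement in the SAP. Giving patients without an arrest their own category is coding and is not forbidden by the rule, though the SAP does not say it will be done.

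Other objections also stand:

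- The loss depends only on the covariates in the given model. Age, sex, body weight, infarct type and ventilation on admission are entered before allocation, so a model with only these should lose few or no patients.
- Every missingness rate above is assumed, and if sick patients lack several items at once, independence overstates the loss.
- Complete-case analysis is common in exploratory work, and no confirmatory result depends on it.

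One objection stands only in part. Validation of data collection describes monthly completeness reports and source checks. The completeness checks cover mandatory fields, which the SAP does not identify, and the missing-data rule itself expects some values that cannot be corrected.

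**Conclusion.** The point holds as a low-severity precision issue. The rule has no exception for covariates, so each subgroup-adjusted logistic model and each exploratory logistic or Cox model keeps only patients complete on its own covariates. Randomized patients with known arm and outcome are discarded, and the sample differs between models.

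The size cannot be derived from the SAP. With independent blanks it runs from about 10% of patients lost (5 covariates at 2%, standard error x1.05) to about 40% (10 at 5%, x1.29), and it is smaller if blanks cluster. The chi-square tests of the primary and secondary endpoints, the non-inferiority Z-test and the sample size are unaffected. The documents do not support a claim of bias in the treatment odds ratio.

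**What to change.** In Handling of missing values and outliers, exempt covariates measured before randomization from the no-imputation rule.

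In Additional analyses, state that:

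- a blank in such a covariate does not remove a patient from a model of the treatment effect; it is filled, blind to arm, with the overall mean or mode, and a missing indicator is added;
- structurally absent items are coded from their parent item, for example no arrest as its own category;
- variables possibly measured after randomization, such as first-day LVEF, are not used to adjust the treatment effect;
- the number analysed is reported for every model;
- complete-case results are kept as a sensitivity check.

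The cost is SAP wording and a few lines of code, with no new data. The downside is that coefficients of filled covariates cannot be interpreted in themselves. Where prognostic coefficients are the target, as in the exploratory models of patient characteristics, use multiple imputation instead.
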